## **14.2 General statistical considerations**

Summary statistics will consist of frequency tables for categorical variables. For continuous variables, summary statistics will consist of number of available observations, arithmetic mean, SD, median, minimum, and maximum unless stated otherwise.

All statistical tests will be performed 2-sided at a 5% level of significance unless stated otherwise.

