## **14.3 Planned efficacy analyses**

### **14.3.1 Analysis of the primary and secondary efficacy variables**

A fixed sequence testing procedure will be applied for the primary and selected secondary variables. The testing procedure will control the family-wise type-I-error and will account for multiplicity. The family-wise error will be set to  $\alpha=0.05$  (2-sided).

For each test, on each binary efficacy endpoint, the null hypothesis is that the conditional odds ratio is equal to one.

$H_0: OR_{T1T2} = 1$

The alternative hypothesis is that the conditional odds ratio is not equal to one.

$H_A: OR_{T1T2} \neq 1$

For each test on each continuous efficacy endpoint, the null hypothesis is that there is no difference between treatment groups.

$H_0: T_1 - T_2 = 0$

The alternative hypothesis is that there is a difference between treatment groups.

$H_A: T_1 - T_2 \neq 0$

[figure not shown]
For the primary and secondary variables, the primary comparison is the bimekizumab 160mg sc Q4W vs placebo. Point estimates and 95% confidence intervals (CI) will be calculated.

No formal statistical comparisons will be made with the adalimumab 40mg sc Q2W treatment group.

The testing starts with  $H_1$ . If  $H_1$  can be rejected at  $\alpha=0.05$  (2-sided), the corresponding  $\alpha$  will be passed on to the next test in the sequence and testing will continue. The testing will be stopped if a hypothesis cannot be rejected at  $\alpha=0.05$  (2-sided).

The fixed sequence testing procedure of primary and secondary efficacy endpoints is shown in Figure 14-1.

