3. Intercurrent event handling = An intercurrent event is defined as discontinuation of study treatment prior to Week 16. A hypothetical strategy for addressing intercurrent events will be implemented. This estimand targets the treatment difference in a scenario where withdrawal from study treatment does not occur, such that outcomes for subjects without an intercurrent event are as observed, and outcomes for subjects with an intercurrent event are treated as though they had completed the randomized study treatment through Week 16. A multiple imputation strategy will be used to impute data following an intercurrent event.
4. Population-level summary measure = the difference in the adjusted means between bimekizumab 160mg Q4W and placebo.

Any missing data at Week 16 that are not preceded by an intercurrent event (ie, discontinuation of study medication) will also be imputed based on a predefined MI model. In MI, the missing value is replaced by a set of plausible values, where each value is a Bayesian draw from the conditional distribution of the missing data given the observed data. Intermittent missing data will be imputed using the MCMC method, followed by monotone regression for monotone missing data.

In the case of vdHmTSS missing data, as vdHmTSS is only collected at Baseline prior to Week 16; missing data at Week 16 will be imputed using monotone regression.

The statistical model for continuous endpoints for the comparison of bimekizumab and placebo will be an ANCOVA model with treatment, bone erosion, and region as fixed effects and the

---

Baseline value as covariate. The statistical hypothesis for the continuous variables at Week 16 is that the treatment difference between the bimekizumab treatment group and placebo is equal to 0.

All secondary efficacy variables will also be summarized based on observed case data as well as multiple imputation using the modified composite estimand for binary variables.

Variables that are included in the hierarchy will additionally be rerun using the COVID-19-free Set.

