## **14.9 Determination of sample size**

Approximately 840 subjects will be randomly assigned in a 3:2:1 ratio to the following treatment groups: bimekizumab 160mg sc Q4W (420 subjects), placebo (280 subjects), adalimumab 40mg sc Q2W (140 subjects).

The primary efficacy analysis is based on the bimekizumab dose versus placebo for ACR50 response at Week 16. It is planned that only descriptive summaries will be provided for the adalimumab reference arm. No statistical comparisons will be made between adalimumab and the other treatment groups.

All sample size and power calculations were done at a significance level of 0.05.

All sample size and power calculations were performed using the software nQuery Advisor® 7.0.

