### **14.9.2 Power calculations for secondary endpoints**

The assumptions for power calculations of the secondary endpoints included in the hierarchy, and for which supporting data exists, are based on the interim results of the Phase 2b

---

bimekizumab study PA0008 and the FUTURE 1, FUTURE 2, FUTURE 5, and SPIRIT P1 studies. All power calculations for binary endpoints were performed using a 2-sided 2-sample Chi-square test with continuity correction (Fleiss et al, 1980). All power calculations for continuous endpoints were performed using a 2-sided 2-group Satterthwaite t-test (Moser et al, 1989).

For the PASI90 response at Week 16, the bimekizumab 160mg Q4W treatment response at Week 12 is 45% (n=20) in the TNF $\alpha$ -naïve population of PA0008 at Week 12 and 46% (n=28) at Week 12 in the mixed TNF $\alpha$  exposure population. The placebo PASI90 response at Week 16 is based on the subgroup analyses of TNF $\alpha$  therapy-naïve subjects in PA0008 (9.1% at Week 12; n=22), FUTURE 2 study (9.7% at Week 24; n=63), and SPIRIT P1 study (1.5% at Week 12; n=67). Therefore, a placebo PASI90 response rate of 10% is assumed. With those assumptions, the study has >99% power to detect a true treatment difference at an assumed 60% of subjects with BSA  $\geq$ 3% of the planned sample size.

For change from Baseline in HAQ-DI at Week 16, the between treatment differences of the change from Baseline in HAQ-DI of in the mixed TNF $\alpha$  exposure population of the PA0008 at Week 12 were used. The bimekizumab 160mg Q4W treatment group mean change from Baseline in HAQ-DI at Week 12 of -0.37, SD=0.47 (n=41) versus placebo mean change from Baseline in HAQ-DI at Week 12 of -0.13, SD=0.50 (n=42). With those assumptions, the study has >99% power to detect a true treatment difference of -0.24 at the planned sample size.

For change from Baseline in PCS of SF-36 at Week 16, the between treatment differences of the change from Baseline in PCS of SF-36 of the TNF $\alpha$ -naïve population of FUTURE 2 study (Kavanaugh et al, 2016) at Week 24 were used. The bimekizumab 160mg Q4W treatment group assumes the secukinumab 150mg treatment group mean change from Baseline in SF-36 PCS at Week 24 of 7.91, SD 7.38 (N=63) versus placebo mean change from Baseline in SF-36 PCS at Week 24 of 2.08, SD 9.51 (N=63). With those assumptions, the study has >99% power to detect a true treatment difference of 5.83 at the planned sample size.

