**Table 14–1: Treatment effect by elevated hs-CRP and/or bone erosion at Baseline for secondary efficacy analyses**

Subjects with elevated hs-CRP and/or bone erosion at Baseline	Treatment difference/standard deviation	
	Treatment effect = -0.3 SD=0.72 vs 0.71	Treatment effect = -0.35 SD=0.81 vs 0.93
20%	67	62
25%	76	72
30%	84	79
35%	89	85
40%	92	89
45%	95	92
50%	96	95

hs-CRP=high sensitivity C-reactive protein; SD=standard deviation

For enthesis free-state at Week 16, enthesis resolution data from the FUTURE 5 study at Week 16 were used to estimate the bimekizumab 160mg Q4W treatment and placebo groups. In FUTURE 5 The treatment effect estimate from the secukinumab 150mg treatment group at Week 16 was 55% (n=141) and the placebo group estimate was 36% (n=192). Assuming a BKZ response of 55% and a placebo rate of 39% and having 25% of subjects with Baseline enthesis the pooled PA0010/PA0011 the studies have a 69% power to detect a true treatment difference of 16% (odds ratio 1.91).

For dactylitis-free state at Week 16, dactylitis resolution data of the FUTURE 5 study (Mease et al, 2018) at Week 16 were used to estimate the bimekizumab 160mg Q4W treatment and placebo groups. The treatment effect estimate from the secukinumab 150mg treatment group at Week 16 of 56% (n=103) is assumed versus a placebo group estimate of 32% (n=124). With those assumptions and having 11% of subjects with Baseline dactylitis, the pooled PA0010/PA0011 studies have a 66% power to detect a true treatment difference of 24% (odds ratio 2.71).

Treatment difference in change from Baseline in vdHmTSS at Week 16 in the overall population is estimated using the data from the FUTURE 5 study in a mixed TNF $\alpha$  exposure population. The bimekizumab 160mg Q4W group treatment difference compared to placebo is estimated to be the same as the difference in change from Baseline in vdHmTSS at Week 16 between the secukinumab 150mg group and placebo which is 0.42, assuming a SD of 1.13 for bimekizumab and SD=2.44 for placebo. With these assumptions the study has 76% power to detect a treatment difference of 0.42 in the planned sample size.

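### Overall-population vdHmTSS is powered with an unequal-variance test but analysed by an ordinary ANCOVA; under the protocol's own SDs the nominal 5% test has a size of about 8.5%

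*Protocol*

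**What the plan says.** - **Analysis.** For the continuous variables in the testing hierarchy (HAQ-DI, SF-36 PCS, vdHmTSS), Section 14.3.1.2 says the "comparison of bimekizumab and placebo will be an ANCOVA model with treatment, bone erosion, and region as fixed effects", with the Baseline value as covariate, after multiple imputation. It gives no residual-variance structure and no standard-error estimator.
- **Power method.** Section 14.9.2: "All power calculations for continuous endpoints were performed using a 2-sided 2-group Satterthwaite t-test".
- **Power inputs.** For vdHmTSS in the overall population, Section 14.9.2 takes a difference of 0.42, "assuming a SD of 1.13 for bimekizumab and SD=2.44 for placebo", and concludes that "the study has 76% power to detect a treatment difference of 0.42 in the planned sample size".
- **Arm sizes.** Section 14.9: "bimekizumab 160mg sc Q4W (420 subjects), placebo (280 subjects), adalimumab 40mg sc Q2W (140 subjects").
- **Error control.** Section 14.2: "All statistical tests will be performed 2-sided at a 5% level of significance unless stated otherwise". Section 14.3.1: "The testing procedure will control the family-wise type-I-error and will account for multiplicity", with the family-wise level set at 0.05 two-sided. For continuous endpoints the null hypothesis in that section is a zero difference between treatment groups, and 95% confidence intervals are to be reported.
- **Two vdHmTSS hypotheses.** Section 4.2.1 lists vdHmTSS twice: in subjects with elevated hs-CRP and/or at least one erosion, and in the overall population. This point concerns the second.

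**The concern.** An ordinary ANCOVA pools the residual variance over the arms. Pooling does little harm when the arms are equal in size or in variance. Here they differ in both, and in the unfavourable direction: placebo is planned to have the larger SD and the fewer subjects. The pooled estimate is then dominated by the larger, quieter bimekizumab arm and understates the uncertainty of the placebo mean, which drives the standard error of the difference.

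At stake are a confidence interval that is too narrow and a p-value that is too small for a structural-damage claim, within a sequence for which the protocol asserts 5% family-wise control. The planning step allowed for unequal variances and the stated analysis, read in the usual way, does not. The quoted power therefore belongs to a different test from the one to be run.

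**Working it through.** **Inputs.** n = 420 (bimekizumab) and 280 (placebo), Section 14.9. SD 1.13 and 2.44, difference 0.42, stated power 76%, Section 14.9.2. Two-sided alpha 0.05, Section 14.2. The SD ratio is 2.44/1.13 = 2.16 and the variance ratio is 4.7.

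**Step 1: reproduce the stated power.**
- Unequal-variance SE = √(1.13²/420 + 2.44²/280) = √(0.00304 + 0.02126) = 0.1559.
- 0.42/0.1559 = 2.69. The Satterthwaite test (about 360 df, noncentral t) has power 76.6%, against 76% stated.
- A pooled-variance calculation gives 86.6% if its SE is taken as true, so it does not reproduce the figure. The 76% rests on the unequal-variance test.

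**Step 2: size of the common-variance test.**
- Pooled variance = (419 × 1.13² + 279 × 2.44²)/698 = 3.146; pooled SD 1.774.
- Model SE = √(3.146 × (1/420 + 1/280)) = 0.1368.
- Ratio of model SE to true SE = 0.1368/0.1559 = 0.878.
- Size = 2 × (1 − Φ(1.963 × 0.878)) = 2 × (1 − Φ(1.724)) = 8.5%. Coverage of the 95% CI is 100% − 8.5% = 91.5%.
- At the planned difference the test rejects with probability Φ(2.69 − 1.72) = about 83%. The excess over 76% comes from the understated SE.

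**Step 3: allocation is what makes it harmful.** With the same SDs and 350 per arm the size would be 5.0%. With the larger SD in the larger arm it would be 2.5%.

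**Step 4: simulation.** ANCOVAs with treatment, erosion, four regions and a baseline covariate were simulated under equal means (10,000 runs per scenario).

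| Scenario (SD 1.13 vs 2.44) | Ordinary SE | HC3 SE |
|---|---|---|
| Normal errors | 8.1% | 4.6% |
| Baseline R² = 0.3 | 8.6% | 5.1% |
| Skewed errors | 8.9% | 5.9% |

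At the planned difference of 0.42 (5,000 runs), the ordinary SE rejects in 83.2% and HC3 in 76.5%. Multiple imputation was not simulated.

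**Step 5: the other continuous hierarchy endpoints**, by the formula of Step 2.

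| Endpoint | SDs (bimekizumab vs placebo) | Size at nominal 5% |
|---|---|---|
| vdHmTSS, hs-CRP/erosion subgroup (45%: 189 vs 126) | 0.72 vs 0.71 | 4.8% |
| Same, alternative column of Table 14-1 | 0.81 vs 0.93 | 5.6% |
| HAQ-DI | 0.47 vs 0.50 | 5.2% |
| SF-36 PCS | 7.38 vs 9.51 | 6.2% |

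**Step 6: if adalimumab enters the same model.** The protocol does not say whether the 140 adalimumab subjects contribute to the residual variance. If they do, the overall vdHmTSS size runs from 6.5% (assumed adalimumab SD 2.44) to 10.2% (assumed SD 1.13).

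**The case against.** **The protocol never says equal variance, and the SAP may set the estimator.** True. Common variance is the standard reading of an ANCOVA described only by its mean terms, not a stated term, and nothing in Section 14.3.1.2 forbids a robust estimator. Powering with a simpler test than the analysis model is also ordinary practice; the binary endpoints use a chi-square test for power and logistic regression for analysis. The mismatch alone is therefore no error. What remains is that the stated model, run in its usual form on the protocol's own figures, misses its nominal level.

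**The SDs are borrowed.** True. They come from a secukinumab trial with mixed TNF exposure, whereas this trial enrols biologic-naïve subjects, and they are not shown to be covariate-adjusted residual SDs. The 8.5% is conditional on them.

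**If the drug did nothing to structure, both arms would share one distribution and the size would be 5%.** Also true. But the null in Section 14.3.1 is a zero mean difference, not identical distributions, and the CI under-covers at any true difference if the SDs differ as planned.

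**A reader might infer that the family-wise error is 8.5%.** The documents do not support that as a general statement. In the order of Section 4.2.1 (Figure 14-1 is not shown), this test follows the subgroup vdHmTSS (power 95%), enthesitis (69%) and dactylitis (66%) tests. Taking the remaining tests, at over 99%, as passed and assuming independence, it is reached with probability 0.95 × 0.69 × 0.66 = 0.43. Its false-positive contribution is then about 0.43 × 8.5% = 3.7%. Control at 5% must, however, hold for every combination of true and false nulls. When the earlier effects are large and this null is true, the error approaches 8.5%.

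**A reader might also extend the finding to every vdHmTSS and SF-36 test.** Step 5 rules that out: the subgroup vdHmTSS test runs at about 5%. The SF-36 PCS excess is small and changes no likely decision with power above 99%.

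**Conclusion.** The point holds for change from Baseline in vdHmTSS at Week 16 in the overall population. Under an ordinary common-variance ANCOVA, the planning SDs of 1.13 and 2.44, 420 and 280 subjects, and equal means, the nominal 5% test has a size of about 8.5% and the 95% CI covers about 91.5%. The consequence for the family-wise error arises only when the earlier hierarchy tests are passed.

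The subgroup vdHmTSS test and HAQ-DI are essentially unaffected, SF-36 PCS is minor, and the primary ACR50 analysis is untouched. The stated 76% power is correct for the test used to compute it. This should be fixed, but it is not a must-fix: it concerns one secondary hypothesis, depends on borrowed SDs, and rests on the usual reading of ANCOVA rather than an explicit statement.

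**What to change.** In Section 14.3.1.2, and carried into the SAP, keep the ANCOVA mean model (treatment, bone erosion, region, Baseline value). Add that, for the continuous hierarchy endpoints, each imputed data set is analysed either with arm-specific residual variances and Satterthwaite degrees of freedom or with HC3 standard errors, and the results are then combined by Rubin's rules. One of the two should be named in advance.

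This brings the size back to about 5% (4.6% to 5.9% in the HC3 simulations) and puts the analysis on the same footing as the stated 76% power. Arm-specific variances also keep the adalimumab SD from entering the variance of the bimekizumab–placebo contrast.

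The cost is one sentence and one model option. If the planning SDs hold, the overall vdHmTSS interval becomes about 14% wider (0.1559/0.1368 = 1.14). The rejection rate at the planned effect falls from about 83% to about 76% to 77%, the level the protocol already claims. If the variances prove similar, little is lost.

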### **4.2 Secondary variables**

#### **4.2.1 Secondary efficacy variables**

The secondary efficacy variables for this study are as follows:

- Change from Baseline in Health Assessment Questionnaire—Disability Index (HAQ-DI) at Week 16
- PASI90 response at Week 4 and Week 16 in the subgroup of subjects with PSO involving at least 3% BSA at Baseline
- Change from Baseline in the Short Form 36-item Health Survey (SF-36) Physical Component Summary (PCS) at Week 16
- Minimal Disease Activity (MDA) response at Week 16
- Change from Baseline in Van der Heijde modified Total Sharp Score (vdHmTSS) in subjects with elevated hs-CRP and/or at least 1 bone erosion at Baseline at Week 16
- Enthesitis-free state in the Leeds Enthesitis Index (LEI) at Week 16 in the subgroup of subjects with enthesitis at Baseline in the pooled population of PA0010 and PA0011
- Dactylitis-free state based on the Leeds Dactylitis Index (LDI) at Week 16 in the subgroup of subjects with dactylitis at Baseline in the pooled population of PA0010 and PA0011
- Change from Baseline in vdHmTSS in the overall population at Week 16

- ACR20 response at Week 16
- ACR70 response at Week 16
- Proportion of subjects with an Investigator Global Assessment (IGA) score of 0 (clear) or 1 (almost clear) AND at least a 2-grade reduction from Baseline at Week 4 and Week 16 in the subset of subjects with psoriatic skin lesions at Baseline
- Change from Baseline in the Patient's Assessment of Arthritis Pain (PtAAP) at Week 16
- Enthesitis-free state based on the Spondyloarthritis Research Consortium of Canada (SPARCC) index at Week 16 in the subgroup of subjects with enthesitis at Baseline
- Change from Baseline in Psoriatic Arthritis Impact of Disease-12 (PsAID-12) total score at Week 16

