## **5.7 Planned number of subjects and sites**

Approximately 840 subjects will be randomly assigned in a 3:2:1 ratio (stratified by region and bone erosion [ $0, \geq 1$ ]) to the following treatment groups: bimekizumab 160mg sc Q4W (420 subjects), placebo (280 subjects), and adalimumab 40mg sc Q2W (140 subjects). The planned number of study sites is approximately 150.

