### **5.7.1 Enrollment of hs-CRP/bone erosion positive subjects**

It is planned to enroll a minimum of 45% of subjects who are positive for elevated hs-CRP (hs-CRP  $\geq 6$ mg/L) and/or who have at least 1 bone erosion at Screening.

---

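### Both vdHmTSS ANCOVAs leave out Baseline hs-CRP, the trial's other radiographic-risk marker; adding it is a low-cost, optional gain in precision

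*Protocol*

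**What the plan says.** Section 14.3.1.2 states the model for continuous endpoints without qualification. It "will be an ANCOVA model with treatment, bone erosion, and region as fixed effects and the" "Baseline value as covariate". For the radiographic endpoint, that covariate is Baseline vdHmTSS. The wording is firmer than for the primary endpoint, where Section 14.3.1.1 adds the stratification factors only if they prove suitable.

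Two vdHmTSS tests use this model. Section 4.2.1 lists one "in subjects with elevated hs-CRP and/or at least 1 bone erosion at Baseline at Week 16" and another in the overall population.

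hs-CRP has a place in the design. Section 5.7.1 says "It is planned to enroll a minimum of 45% of subjects who are positive for elevated hs-CRP" (at least 6 mg/L), or who have an erosion, or both. It is not a randomization factor: Section 5.7 has subjects "randomly assigned in a 3:2:1 ratio (stratified by region and bone erosion" only. It is measured in every subject at Baseline (Section 8.1.2), and Section 14.3.3 already splits it at 6 mg/L for subgroup analyses.

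On power, Section 14.9.2 gives 95% for the subset test at 45% prevalence. Of the overall test it says "With these assumptions the study has 76% power to detect a treatment difference of 0.42 in the planned sample size". The same section bases its power figures for continuous endpoints on a two-group Satterthwaite t-test.

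**The concern.** The protocol selects subjects for radiographic risk on two markers, and the vdHmTSS model adjusts for only one of them. The disease terms it does carry overlap: vdHmTSS itself scores erosions and joint space narrowing (Section 9.11), so Baseline vdHmTSS and the erosion factor both describe existing structural damage. No term represents inflammation, which is the other half of the enrichment definition.

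If hs-CRP predicts progression over 16 weeks, that variation stays in the error term of two confirmatory tests. Neither design nor model then deals with a chance difference in hs-CRP between arms. The protocol already tailors covariates to the endpoint, since it drops bone erosion for skin outcomes, so an extra term for the radiographic endpoint would fit its own approach.

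**Working it through.** **Inputs.** All are from Sections 14.9 and 14.9.2 unless marked as assumed. "All sample size and power calculations were done at a significance level of 0.05", and the t-test is 2-sided.

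- Overall population: n = 420 and 280, difference 0.42, SD 1.13 and 2.44.
- Subset at 45%: n = 0.45 × 420 = 189 and 0.45 × 280 = 126, difference 0.30, SD 0.72 and 0.71.
- Share of remaining variance explained by hs-CRP (partial R²): not in the protocol, so assumed at 1%, 5% and 10%.

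**Step 1: reproduce the stated powers.** SE = √(SD₁²/n₁ + SD₂²/n₂), with power from the noncentral t distribution on Satterthwaite degrees of freedom.

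- Overall: SE = √(1.13²/420 + 2.44²/280) = √(0.00304 + 0.02126) = 0.1559; df = 359.6; 0.42/0.1559 = 2.69. Power is 76.6%, against 76% stated.
- Subset: SE = √(0.72²/189 + 0.71²/126) = √(0.00274 + 0.00400) = 0.0821; 0.30/0.0821 = 3.65. Power is 95.4%, against 95% stated.

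Both figures are reproduced with no covariate in the calculation. Leaving hs-CRP out of the ANCOVA therefore cannot have lowered either one.

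**Step 2: add hs-CRP.** Multiply both variances by (1 − R²) and recompute. The equivalent sample size is 700/(1 − R²).

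| Assumed R² | Overall power | Subset power | Equivalent n, overall |
|---|---|---|---|
| 0 | 76.6% | 95.4% | 700 |
| 1% | 77.1% | 95.5% | 707 |
| 5% | 78.7% | 96.2% | 737 |
| 10% | 80.8% | 97.0% | 778 |

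Reaching 80% in the overall test needs an R² of about 8%, which is a partial correlation of about 0.28.

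**Step 3: what a binary flag might explain.** Assume that 30% to 60% of subjects are at or above 6 mg/L and that their mean progression is 0.1 to 0.5 units higher. The variance explained is p(1 − p)m². The largest value on the grid used (p = 30%, 45%, 60%) is 0.45 × 0.55 × 0.5² = 0.062. Against a pooled variance of 1.774² = 3.15, that is about 2%. Over the whole assumed range, R² is about 0.1% to 2% and overall power is 76.7% to 77.3%.

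**Step 4: chance imbalance.** Assume 50% prevalence and simple randomization. The 95% range for the between-arm difference in prevalence is 1.96 × √(0.25 × (1/420 + 1/280)) = ±7.6 percentage points overall, and 1.96 × √(0.25 × (1/189 + 1/126)) = ±11.3 points in the subset. With a 0.5-unit difference in mean progression, 7.6 points would shift the overall estimate by 0.076 × 0.5 = 0.038, against an SE of 0.156.

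**Step 5: form of the covariate.** Subset members have elevated hs-CRP, an erosion, or both. Every erosion-negative member is therefore hs-CRP positive, and a 6 mg/L flag varies only among erosion-positive members. Continuous hs-CRP varies in both groups.

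**The case against.** The strongest reply is that nothing here is an error. The model adjusts for both randomization strata and the Baseline score. In a randomized comparison, omitting an unstratified prognostic covariate causes no bias and no type I error inflation, because the test's error rate already allows for chance imbalance. Almost any ANCOVA could take one more covariate. All of this stands.

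Three further points also stand:

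- The protocol gives no association between hs-CRP and vdHmTSS change. That hs-CRP predicts progression is an inference from the enrichment rule.
- The gain is only what hs-CRP explains beyond Baseline vdHmTSS, erosion and region. Those terms may already lift actual power above 76%.
- Enthesitis (69%) and dactylitis (66%) have lower stated powers. Both precede overall vdHmTSS in the Section 4.2.1 list. If the testing order follows that list (Figure 14-1 is not shown), a gain in the overall test counts only once both have succeeded.

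A reader might also infer that the imputation rule wrongly leaves out hs-CRP, because Section 14.3.1.2 says "missing data at Week 16 will be imputed using monotone regression" and mentions only Baseline as an earlier vdHmTSS time point. The text does not support that. The remark about Baseline explains why the monotone method is used; it does not list predictors, and those may properly be left to the SAP.

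The reply does not remove the case for acting. The covariate list is stated outright, so it is a protocol choice. The marker is already collected, and adding it after unblinding would not be credible.

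**Conclusion.** The point holds as a free improvement of low severity. The vdHmTSS model omits a Baseline marker on which the trial itself enriches and which randomization does not balance, so some precision and some protection against chance imbalance may be forgone.

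The tempting stronger reading is that the omission costs power on a test that has only 76%. The documents do not support it. The 76% is an unadjusted figure and belongs to the overall-population test; the test in the subset defined by hs-CRP or erosion has 95%.

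For the overall test, the possible gain is about 0.5 points at an R² of 1%, 2.1 at 5% and 4.2 at 10%. For the subset it is at most about 1.6 points over the same range. These sizes rest on an assumed R² and treat the protocol's SDs as the residual SDs before hs-CRP is added. If hs-CRP proves uninformative, the gain is nil.

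**What to change.** Before unblinding, add one sentence to Section 14.3.1.2: both vdHmTSS ANCOVAs also include Baseline log hs-CRP as a covariate. Use the continuous form because the 6 mg/L flag is constant among erosion-negative members of the subset. State how values below the assay limit and missing Baseline values are handled; a Screening hs-CRP is available under Section 8.1.1.

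When the SAP specifies the imputation model for Week 16 vdHmTSS, include the same covariate so that it matches the analysis model.

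The cost is one degree of freedom among about 700 subjects (about 315 in the subset at 45% prevalence), with no new data collection and no change to the testing sequence or sample size.
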